## **10. SUPPORTING DOCUMENTATION AND OPERATIONAL CONSIDERATIONS**

### **10.1. Ethical and Administrative Obligations**

#### **10.1.1. Regulatory and Ethical Considerations**

This clinical study was designed and shall be implemented and reported in accordance with the International Conference on Harmonisation (ICH) Harmonized Tripartite Guidelines for Good Clinical Practice, with applicable local regulations (including European Directive 2001/20/EC and US Code of Federal Regulations (CFR) Title 21), and with the ethical principles that originate from the Declaration of Helsinki.

The protocol and the proposed ICF(s) must be reviewed and approved by a properly constituted IRB/IEC before study start. Prior to study start, the Investigator is required to sign a protocol signature page confirming his/her agreement to conduct the study in accordance with these documents and all of the instructions and procedures found in this protocol and to give access to all relevant data and records to Karyopharm monitors, auditors, designated agents of Karyopharm, IRBs/IECs, and regulatory authorities as required.

Any amendments to the protocol will require IRB/IEC approval before implementation of changes made to the study design, except for changes necessary to eliminate an immediate hazard to study patients.

#### **10.1.2. Responsibilities of the Investigator and Good Clinical Practice**

The Investigator will be responsible for the following:

- Providing written summaries of the status of the study to the IRB/IEC annually or more frequently in accordance with the requirements, policies, and procedures established by the IRB/IEC
- Notifying the IRB/IEC of SAEs or other significant safety findings as required by IRB/IEC procedures
- Providing oversight of the conduct of the study at the site and adherence to requirements of 21 CFR, ICH guidelines, the IRB/IEC, European regulation 536/2014 for clinical studies (if applicable), and all other applicable local regulations

### **10.2. Financial Disclosure**

Investigators and sub-investigators will provide the sponsor with sufficient, accurate financial information as requested to allow the sponsor to submit complete and accurate financial certification or disclosure statements to the appropriate regulatory authorities. Investigators are responsible for providing information on financial interests during the course of the study and for 1 year after completion of the study.

### **10.3. Informed Consent Process**

The Informed Consent Form (ICF) and the process to obtain the informed consent will comply with all local laws, regulations, and guidance. Karyopharm will provide to Investigators, in a separate document, proposed ICFs that are considered appropriate for this study and comply with

the ICH GCP guidelines and regulatory requirements. Any changes to the ICFs suggested by the Investigator must be agreed to by Karyopharm before submission to the IRB/IEC, and a copy of the approved version(s) must be provided to the Karyopharm after IRB/IEC approval.

All patients, proxies or legal guardians must provide signed written or verbal informed consent as follows:

- In a COVID-19 clinical trial, informed consent may be verbal in the presence of another hospital employee and/or a patient representative. In this case informed consent will be documented in the patient's chart and informed consent will be obtained per usual practice when the patient or patient's representative is able to provide after contamination concerns are no longer an issue.
- In a COVID-19 clinical trial, if a patient is in an emergency situation informed consent will be obtained consistent with 21 CFR 50.24.

Females of childbearing potential should be informed that taking the study drug may involve unknown risks to the fetus if pregnancy were to occur during the study and agree that in order to participate in the study they must adhere to the contraception requirement for the duration of the study and for 3 months after the last dose. If there is any question that the patient will not reliably comply, they should not be entered in the study.

- The investigator or his/her representative will explain the nature of the study to the patient or his/her legally authorized representative or proxy and answer all questions regarding the study.
- Patients must be informed that their participation is voluntary. Patients or their legally authorized representative will be required to sign a statement of informed consent that meets the requirements of 21 CFR 50, local regulations, ICH guidelines, Health Insurance Portability and Accountability Act (HIPAA) requirements, where applicable, and the IRB/IEC or study center.
- The medical record must include a statement that written informed consent was obtained before the patient was enrolled in the study and the date the written consent was obtained. The authorized person obtaining the informed consent must also sign the ICF.
- Patients must be re-consented to the most current version of the ICF(s) during their participation in the study.
- A copy of the ICF(s) must be provided to the patient or the patient's legally authorized representative.

Males should be informed that taking the study drug may lead to reductions in sperm counts, including marked reductions. Recovery from this may take weeks or months and may not be complete and the effects on sperm during recovery are not known. In order to participate in the study, males must adhere to the contraception requirement for the duration of the study and for 3 months after the last dose. If there is any question that the patient will not reliably comply, they should not be entered in the study.

## **10.4. Data Collection and Management**

### **10.4.1. Data Confidentiality**

Patients will be assigned a unique identifier by the Karyopharm. Signed ICFs and patient enrollment logs must be kept strictly confidential to enable patient identification at the site.

Any patient records or datasets that are transferred to Karyopharm will contain the identifier only; patient names or any information which would make the patient identifiable will not be transferred.

Information about study patients will be kept confidential and managed under the applicable laws and regulations. Those regulations require a signed patient authorization informing the patient of the following:

- What protected health information (PHI) will be collected from patients in this study
- Who will have access to that information and why.
- Who will use or disclose that information.
- The rights of a research patient to revoke their authorization for use of their PHI.

In the event that a patient revokes authorization to collect or use PHI, the Investigator, by regulation, retains the ability to use all information collected prior to the revocation of patient authorization. For patients that have revoked authorization to collect or use PHI, attempts should be made to obtain permission to collect follow-up safety information (e.g., has the patient experienced any new or worsened AEs) at the end of their scheduled study period.

The data collection system for this study uses built-in security features to encrypt all data for transmission in both directions, preventing unauthorized access to confidential patient information. Access to the system will be controlled by a sequence of individually assigned user identification codes and passwords, made available only to authorized personnel who have completed prerequisite training.

### **10.4.2. Site Monitoring**

Before site activation, Karyopharm personnel (or designated contract research organization [CRO]) will review the protocol and applicable study documents with the Investigators and their staff (e.g., at a site initiation visit). During the study, the monitor must have access to the source documents to check the completeness of patient records, accuracy of entries on the CRFs, adherence to the protocol and to Good Clinical Practice (GCP), progress of enrollment, and to ensure that study treatment is being stored, dispensed, and accounted for according to specifications. Key study personnel must be available to assist the monitor during these visits. Remote study monitoring could be used, more details will be provided in the study-specific monitoring plan.

The Investigator must maintain source documents for each patient in the study, consisting of case and visit notes (hospital or clinic medical records) containing demographic and medical information, laboratory data, ECGs, and the results of any other tests or assessments. All information recorded on CRFs must be traceable to source documents in the patient's file. The Investigator must also keep the original signed ICF (a signed copy is given to the patient).

The Investigator must give the monitor access to all relevant source documents to confirm their consistency with the CRF entries. Karyopharm monitoring standards require full verification for the presence of informed consent, adherence to the inclusion/exclusion criteria and documentation of SAEs. Additional checks of the consistency of the source data with the CRFs are performed according to the study-specific monitoring plan.

#### **10.4.3. Data Collection**

This study will utilize electronic data capture (EDC), the designated clinical site staff will enter the data required by the protocol into the eCRF. The eCRFs will be constructed using fully validated secure web-enabled software that conforms to 21 CFR Part 11 requirements. Clinical site staff will not be given access to the EDC system until they have been trained. Automatic validation programs check for data discrepancies in the eCRFs and allow modification or verification of the entered data by the Investigator staff. Any missing data must be explained. An audit trail will be maintained by the eCRF system

The Investigator is responsible for assuring that the data entered into the eCRF is complete and accurate, and that entry and updates are performed in a timely manner.

Concomitant treatments and prior medications entered into the database will be coded using the WHO Drug Reference List, which employs the Anatomical Therapeutic Chemical (ATC) classification system. Medical history/current medical conditions and AEs will be coded using the MedDRA terminology.

#### **10.4.4. Database Management and Quality Control**

Karyopharm personnel (or designated CRO) will review the eCRF data entered by investigational staff for completeness and accuracy. Electronic data queries stating the nature of the problem and requesting clarification will be created for discrepancies and missing values and sent to the investigational site via the electronic data capture (EDC) system. Designated Investigator site staff are required to respond promptly to queries and to make any necessary changes to the data.

At the conclusion of the study, after discrepancies and missing values have been completed and the data have been verified to be complete and accurate, the database will be declared locked.

For EDC studies, after database lock, the Investigator will receive a CD-ROM or paper copies of the patient data for archiving at the investigational site.

#### **10.5. Data Safety Monitoring Committee**

At the interim analyses, primary efficacy outcome and/or safety outcomes will be reviewed by the DSMB to determine if the trial will be stopped for futility or efficacy or continue as planned (Section 9.5). The DSMB will meet at least three times during the course of the study.

Enrollment will be paused for evaluation of safety and efficacy after the enrollment of the first 40 patients and the first meeting of the DSMB will occur within the first week of enrolling the 40th patient. No further patients will be enrolled until the completion of this DSMB review and the safety and efficacy data from the first 40 patients will be shared with the FDA prior to resuming enrollment. The remaining DSMB meetings are planned to evaluate the data from the IA. The DSMB may also meet at other times during the study as needed.

The independent DSMB will be composed of at least 3 members who are independent of Karyopharm and the study. The DSMB will meet to evaluate safety and efficacy, to ensure the appropriate benefit risk profile for patients enrolled in the study and to review any SAEs that occur during the study. The DSMB will be provided with all reports of AEs including SAEs regardless of Investigator causality assessments.

Details on how the DSMB will review safety and response data are provided in the DSMB Charter. The DSMB review will include, but not be limited to, evaluations of duration of therapy and all cause and AE-related dose reductions, interruptions, and discontinuations. At the interim analyses, primary efficacy outcome and selected safety outcomes will be reviewed by the DSMB to determine if the trial will be stopped for futility or efficacy or continue as planned.

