## 9.6. Interim Analyses

The first IA occurs 14 days after approximately 74 patients are randomized. This IA is for futility only. The futility boundary p-value will be calculated using the Lan DeMets spending function with the O'Brien-Fleming type of boundary based on the actual number of patients who have completed 14 days on study at the time of the IA.

The second IA happens 14 days after approximately 124 patients are randomized. This IA is for futility and sample size reestimation. An unblinded sample size re-estimation (SSR), is planned to be performed at this IA. The unblinded SSR will be based on the method of conditional power (CP). It is defined as the probability to detect a statistically significant difference for the primary endpoint at the end of study given the current data observed at this IA, assuming this interim trend continues. The CP will be calculated for the primary endpoint at this IA using East software with CHW method (Cui 1999).

The odds ratio and associated p-value will be obtained for the primary endpoint OSI between two arms based on the observed data at this IA, then the CP will be calculated using East. The calculated CP will be assigned to one of the 3 zones:

1. favorable ( $CP \geq 80\%$ )
2. promising ( $30\% \leq CP < 80\%$ )
3. unfavorable ( $CP < 30\%$ )

The original planned total sample size of approximately 247 patients will be increased to achieve the targeted power of 80%, up to a maximum of 371 patients when the conditional power is in the promising zone. If the CP is  $<30\%$ , the trial may be stopped for futility (non-binding). Otherwise, if the CP is  $\geq 80\%$  the total sample size will remain at 247 patients, and the trial continues as planned.

If the trial is not stopped at IAs and sample size is not changed based on the second IA, enrollment will continue until approximately 247 patients are enrolled, the final analysis will happen when all enrolled patients have had the chance to have the Day 14 OSI assessed.

At the interim analyses, primary efficacy outcome and selected safety outcomes will be reviewed by the Data Safety Monitoring Board (DSMB) to determine if the trial will be stopped for futility, adjust the sample size, or continue as planned.

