### 2.3 Interim Analyses

[figure not shown]
The interim analyses apply to ITT population only.

The first IA occurs 14 days after the first 74 patients are randomized. This IA is for futility only (non-binding). The futility boundary p-value will be calculated using the Lan DeMets spending function with the O'Brien-Fleming type of boundary based on the actual number of patients who have completed 14 days on study at the time of the IA.

The second IA happens 14 days after 124 patients are randomized. This IA is for futility and sample size re-estimation (SSR). An unblinded SSR is planned to be performed at this IA. The unblinded SSR will be based on the method of conditional power (CP). It is defined as the probability to detect a statistically significant difference for the primary endpoint at the end of study given the current data observed during this second IA, assuming this interim trend continues. The CP will be calculated for the primary endpoint at this IA using East software with CHW method (Cui et al., 1999).

The odds ratio and associated p-value will be obtained for the primary efficacy endpoint between two treatment arms based on the observed data at this IA, then the CP will be calculated using East. The calculated CP will be assigned to one of the 3 zones:

1. favorable ( $CP \geq 80\%$ )
2. promising ( $30\% \leq CP < 80\%$ )
3. unfavorable ( $CP < 30\%$ )

Additionally, if the 2nd interim analysis is conducted and sample size is adjusted, the CHW method (Cui et al., 1999) will be implemented in the primary analysis for the primary and key secondary efficacy endpoints to preserve the overall type I error.

Please refer to Section 9.5 in Protocol for Criteria for Stopping the Study.

[figure not shown]

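### Protocol 10.5 lets the DSMB stop for efficacy at the interims, but Protocol 9.6 and SAP 2.3 provide only for futility and sample size re-estimation

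*Protocol*

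**What the plan says.** Protocol 10.5 states the DSMB's interim decision twice. The first statement says the outcomes are "reviewed by the DSMB to determine if the trial will be stopped for futility or efficacy or continue as planned (Section 9.5"). The second, at the end of the section, says "selected safety outcomes will be reviewed by the DSMB to determine if the trial will be stopped for futility or efficacy" or continue. Sample size does not appear in either.

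Protocol 9.6 gives a different set of options: the DSMB reviews the data "to determine if the trial will be stopped for futility, adjust the sample size, or continue as planned". It describes the first interim, after about 74 patients, with "This IA is for futility only", and the second, after about 124, with "This IA is for futility and sample size reestimation". If conditional power is 80% or more at the second interim, the trial runs on to 247 patients.

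SAP 2.3 assigns the same purposes. For the first interim it says "This IA is for futility only (non-binding"), and for the second it gives futility and re-estimation.

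Only one group sequential boundary is described: "The futility boundary p-value will be calculated using the Lan DeMets spending function". The SAP's error-control step is conditional: "if the 2nd interim analysis is conducted and sample size is adjusted, the CHW method" is used in the primary analysis.

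**The concern.** Section 10.5 is where the protocol sets out the DSMB's remit, and it grants a power that the interim analysis sections do not. The DSMB reviews the primary efficacy outcome at both interims, and the re-estimation at the second is expressly unblinded, so the data for an efficacy decision would be in front of it.

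An early stop for benefit needs a threshold fixed in advance and a final critical value that allows for the earlier looks. The visible plan supplies neither. A futility boundary does not control false positive stops, and the CHW method is invoked only when the sample size changes.

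The omission works the other way too. A DSMB reading 10.5 alone would not learn that at the second interim it must decide whether to raise the sample size, which can go from 247 to 371.

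**Working it through.** **Comparing the sections**

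| Source | Stop for futility | Stop for efficacy | Adjust sample size | Continue |
|---|---|---|---|---|
| Protocol 10.5, both statements | yes | yes | not listed | yes |
| Protocol 9.6, DSMB options | yes | not listed | yes | yes |
| SAP 2.3, purposes of the interims | yes, both | not listed | second interim | implied |

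The cross-reference does not resolve the conflict. Protocol 9.5 holds halting thresholds for excess deaths, invasive ventilation and Grade 3 or 4 nausea or vomiting, plus one sentence on futility. It has no rule for benefit on Day 14 ordinal scale improvement. The interim rules are in 9.6, which 10.5 does not cite.

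**What an unregulated efficacy stop could cost**

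The plan gives no figure to reproduce here, and its alpha and sidedness are not visible. What follows is an illustration on stated assumptions.

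- Looks at 74, 124 and 247 patients (Protocol 9.6). Information fractions: 74/247 = 0.300, 124/247 = 0.502, 1.
- Under the null, the three test statistics are jointly normal with corr(Zi, Zj) = √(ti/tj) for ti < tj.
- Final test at two-sided 0.05 (|z| > 1.96), no sample size change, no futility stopping.
- Overall error = P(interim threshold crossed at either look, or final test significant), by simulation.

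| Interim efficacy threshold | Two-sided, stops in either direction | Two-sided, only benefit stops at interims | One-sided (nominal 2.5%) |
|---|---|---|---|
| p < 0.05 (z = 1.96) | 11.0% | 8.0% | 5.5% |
| p < 0.01 (z = 2.576) | 6.0% | 5.5% | 3.0% |
| z = 3.0 | 5.2% | 5.1% | 2.6% |
| z = 3.29 | 5.1% | 5.0% | 2.5% |

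**What a proper boundary would cost**

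An O'Brien-Fleming-type Lan-DeMets function at one-sided 0.025 spends α(t) = 2[1 − Φ(z₀.₉₈₇₅/√t)]. Cumulative spending is 0.00004 at t = 0.300, 0.0016 at t = 0.502 and 0.025 at t = 1. Solving for the boundary gives z = 3.93, 2.96 and 1.97 (two-sided nominal p = 0.00008, 0.0031 and 0.0490). With the sample size fixed, power falls from 80% to 79.85%, or from 90% to 89.90%.

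**A related sentence in Protocol 9.5**

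The closing sentence of 9.5 has each interim determine whether there is no significant improvement, without a level or an action. Suppose it were read as p > 0.05 at the second interim. Conditional power under the current trend is CP = Φ[(Z/√t − 1.96)/√(1 − t)], with t = 0.502.

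- Z = 1.127 (p = 0.260): CP = Φ[(1.591 − 1.96)/0.706] = 30%.
- Z = 1.810 (p = 0.070): CP = Φ[(2.555 − 1.96)/0.706] = 80%.
- Z = 1.96 (p = 0.05): CP = Φ[(2.766 − 1.96)/0.706] = 87%.

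That reading would put the whole promising zone, where 9.6 calls for more patients, on the futility side.

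**The case against.** The best reply is that this is leftover wording. Sections 9.6 and SAP 2.3 are the operative text, and they agree. In 9.6 even a favorable interim result leads to continuation. Section 10.5 is administrative, sets no procedure of its own and defers details to the DSMB Charter. Its incomplete list of options does not withdraw the sample size step that 9.6 states outright. On this view the missing sample size option is minor, and that is fair: taken alone it would be.

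The error figures are also hypothetical. The 11.0% requires a DSMB willing to stop at nominal p < 0.05 with 30% of the information, and it counts stops in the harm direction; 8.0% is the benefit-only figure. At strict thresholds the excess is negligible. Patient fractions stand in for information although SAP 7.1.1 says about the first 50 ITT patients were randomized 2:1; allowing for that moves the top figure only to about 11.1%. These points limit the size of the concern.

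Finally, a boundary could exist where the reader cannot see it: the sample size text in Protocol 9.2 is redacted, SAP 2.2 is cut off, two figures in SAP 2.3 are not shown, and the Charter is not supplied. That is why the absence of a boundary is claimed for the visible text only. It does not remove the contradiction. An interim described as futility only conflicts with an option to stop for efficacy, whatever those places contain.

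**Conclusion.** The concern holds and should be fixed. Protocol 10.5 twice gives the DSMB an efficacy stop that Protocol 9.6 and SAP 2.3 exclude by their stated purposes, and it omits the sample size decision that 9.6 assigns to the DSMB. Since 9.6 and SAP 2.3 agree, the efficacy wording is probably unintended. It is nevertheless a stated decision rule, and followed literally it allows a claim of benefit without visible error control.

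The practical size runs from almost nothing (5.1% overall with a strict informal threshold) to a serious inflation (11.0%, or 8.0% counting only benefit stops, with unadjusted testing). These figures assume a two-sided 0.05 final test, the planned look times and no sample size change. The visible plan does not say where in that range the trial would fall.

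**What to change.** **If no efficacy stop is intended** (the likelier case): in both sentences of Protocol 10.5 delete *or efficacy*, add sample size adjustment to the options, and cite Section 9.6 as well as 9.5.

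**If an efficacy stop is intended:** prespecify an alpha-spending efficacy boundary in Protocol 9.6 and SAP 2.3 before any unblinded look, and use its final critical value in the final test, including the CHW version if the sample size changes.

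Either way, align the DSMB Charter, and make the last sentence of Protocol 9.5 refer to the futility rules in 9.6.

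The first option costs three sentences of protocol wording and a Charter check, with no effect on power. The second costs an added paragraph in each of 9.6 and SAP 2.3 and, with an O'Brien-Fleming-type boundary, about 0.1 to 0.15 points of power.
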